Endpoints	
 
• All-cause in-hospital mortality
 
• Morbidity at defined post-diagnosis intervals and over 7 consecutive days 
 
- Mean total SOFA score (age <math>\geq 16</math>)
 
- PELOD score (age <math>< 16</math>)
 
- <math>\Delta</math>SOFA or dPELOD score for day-to-day comparisons
 
 
 
• Extent and severity of Purpura lesions
 
• Need for reconstructive surgery (amputations, skin grafts)
 
• Length of ICU stay (days)
 
• Length of hospital stay (days)
 
• Changes in hematological parameters 
 
- WBC count
 
- Thrombocyte count
 
- Hemoglobin
 
 
 
• Changes in coagulation parameters 
 
- Prothrombin time (PT)
 
- Activated partial thromboplastin time (aPTT)
 
- Fibrinogen
 
- D-dimers
 
- Thrombin-antithrombin complex (TATc)
 
- Protein C activity
 
- Antithrombin III activity
 
 
 
• Changes in inflammatory parameters 
 
- C-reactive protein (CRP)
 
- Procalcitonin (PCT)
 
- Interleukin 6 (IL-6)
 
 
 
• Changes in organ dysfunction parameters 
 
- Glucose
 
- Lactate
 
- Creatine kinase (CK)
 
 
 
• Duration of mechanical ventilation (days)
 
• Duration of renal replacement therapy (days)
 
• Vasopressor use (days/doses)
 
• Sepsis-inducing pathogen
 
• Adverse event related to PF treatment (reporting as per decision of the investigator) 
 
- Bleeding
 
- Thrombotic events
 
 
 

Inclusion criteria	
 
- Diagnosis of severe sepsis and Purpura fulminans
 
- Signed informed consent (according to local legal regulations)
 

Exclusion criteria	
 
- premature neonates (<math>< 36</math> gestational week)
 

Centers	Approx. 30 participating centers in Germany, Austria, Ireland, UK, Italy, Spain, Netherlands (selected centers)

Timetable	First patient in	Q3 2015
	Registry duration	3 years, with an option of prolongation
	Estimated enrolment	Approx. 50 patients/year
	Interim Analysis	Biannually

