**Flowchart**

Activity / Endpoint	Baseline 	Post-diagnosis period (days)					End of study at hospital discharge or in-hospital death after ICU discharge
		1	3	5	7	ICU discharge or death on ICU after day 7	
Confirm inclusion criteria	x						
Provision of informed consent 	x						
Demographic data collection (incl. ethnic origin)	x						
Risk factors (vaccination status, asplenia) and comorbidities	x						
Estimated time of SAPF onset (hours)	x						
Mortality prediction (APACHE II/SAPS II  or PRISM III  score)	x						
Morbidity assessment (SOFA  /PELOD  score)	x	x	x	x	x		
Laboratory parameters (hematology, coagulation, inflammation)	x	x	x	x	x		
Purpura lesion assessment (c.f. eCRF)	x	x	x	x	x		
Vasopressor use record	x	x	x	x	x	x	
Site, source and origin of infection (including viral)							x
Concomitant causal, supportive and adjunctive treatment (c.f. eCRF)		x	x	x	x	x	
Cumulative dose of blood products and anti-coagulant treatment		x	x	x	x	x	
Antimicrobials		x	x	x	x	x	
Days in ICU							x
Days on mechanical ventilation							x
ECMO and circulatory support systems		x	x	x	x	x	
Days/type on renal replacement therapy							x
Purpura-related surgery (fasciotomy, debridement, amputation)							x
In-hospital mortality assessment		x	x	x	x	x	x
Days in hospital							x
Adverse drug reactions							x

 admission at ICU; according to local regulations APACHE II/SAPS II and SOFA scores will be used in patients aged above 16 PRISM III and PELOD scores will be used in patients aged below 16

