#### 8.5. Study size

Earlier reports on the incidence of SAPF [Darmstadt, 1998; Nicolas and Debonne, 2002] were based on the association of the condition with meningococcal sepsis. Conceivably, these data hardly permit extrapolation to the contemporary situation, which has substantially changed after the introduction of meningococcal vaccination [Maat et al., 2007]. Depending on the number of participating centers, a realistic forecast envisages the recruitment of 50 to 70 adult and pediatric patients during the first year of the registry, with subsequent possible increase to 100 per year. In view of the spread of meningococcal vaccination among children and adolescents, the expected proportion of adult patients might eventually exceed 50 %.

With regard to the relatively limited projected study size, and with regard to the lack of a uniform treatment concept for SAPF, demonstration of differences between individual treatment paradigms might require dichotomization (e.g. use vs. omission of Protein C supplementation) and could be applicable only to selected endpoints.

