## 8.7. Data analysis

A binary logistic regression model will be fitted for the all-cause in hospital mortality to compare the efficacy of the different treatments (e.g. with or without Protein C supplementation). To adjust for confounders, causal pathogen, baseline Apache II (PRISM III) score, laboratory parameters, age, sex, co-medication etc. can be included as covariates in this model.

Consecutive changes in SOFA or PELOD scores ( $\Delta$ SOFA, dPELOD) at individual post-diagnosis intervals and their mean values calculated for the observation period of 7 days will be compared to the scores determined on admission (baseline). Changes in these organ failure indices will be examined by means of

- Paired samples T-test
- Linear model with morbidity score baseline adjustment and alternative co-variables (e.g. hematological, coagulation or inflammatory parameters)

Explorative analysis without correction and with a pre-set level of significance of 0.05 will be conducted as well.

All endpoints will be subjected to descriptive statistical analysis with determination of 95-percent confidence intervals. Between-group comparisons will be preceded by distribution analysis (Shapiro-Wilk Test of normality). Depending on the data distribution, *post hoc* processing will involve either parametric (one-way ANOVA, T test) or non-parametric (Kruskal-Wallis, Mann-Whitney U-test) approaches.

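### Section 8.7 names no Protein C term for the SOFA/PELOD endpoint and no way to combine the two instruments, although morbidity by Protein C use is a stated objective.

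*Combined protocol and SAP*

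**What the plan says.** Morbidity is scored with two instruments chosen by age. The endpoint list in the Abstract (Section 4) gives "Mean total SOFA score" for age 16 and over and PELOD below 16. The flowchart footnotes in Section 8.2 say "APACHE II/SAPS II and SOFA scores will be used in patients aged above 16" and "PRISM III and PELOD scores will be used in patients aged below 16", which leaves a patient aged exactly 16 unassigned and differs from the Abstract.

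The third objective in the Abstract asks for outcomes, morbidity included, split by whether Protein C was given. Sections 7, 8.1 and 8.2 repeat the comparative aim.

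Section 8.7 says that "Consecutive changes in SOFA or PELOD scores", and their 7-day means, "will be compared to the scores determined on admission (baseline"). The methods listed for this are a paired t-test and a "Linear model with morbidity score baseline adjustment and alternative co-variables (e.g. hematological, coagulation or inflammatory parameters"). The only between-group methods open to these scores come in a general closing paragraph: "Between-group comparisons will be preceded by distribution analysis (Shapiro-Wilk Test of normality"), followed by t-test/ANOVA or Mann-Whitney/Kruskal-Wallis. None is stratified.

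The mortality model in the same section, in contrast, is expressly a treatment comparison and lists candidate confounders, age among them.

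**The concern.** There are two gaps, the first more basic than the second.

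1. **No treatment term.** The methods attached to the scores compare each patient with his or her own admission value. They describe a course over time and do not estimate a difference between Protein C users and non-users, which is what the objective asks for.
2. **No combination rule.** Once a treatment contrast is wanted, the analyst must either run SOFA and PELOD separately, each on part of a registry that Section 8.5 already regards as small, or put both scores into one test. The second route averages points from different scales. Because the physician chooses the treatment (Section 9), the age mix may differ between users and non-users, and the contrast would then partly reflect which instrument was used.

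The choice matters because Section 8.9 itself doubts mortality as a main endpoint in so lethal a condition, which puts more weight on morbidity, and because Section 11 plans treatment recommendations from these evaluations.

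**Working it through.** The plan states no total sample size, effect size, SD or treated share for this endpoint, so there is no figure of its own to reproduce. The following illustrates what a combined contrast would gain.

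**Inputs**
- N = 150: about 50 patients per year for 3 years (Abstract). Upper case N = 270: 70 + 100 + 100 (Section 8.5).
- Adult share: Section 8.5 says only that "the expected proportion of adult patients might eventually exceed 50" per cent. I assume 50%, with 40% and 70% as a range.
- Treated share: not in the documents. I assume 40%, with 30% and 50% as a range, equal in both age groups.
- Alpha 0.05 (Section 8.7), two-sided assumed; power 80% assumed. Multiplier 1.96 + 0.84 = 2.8.
- Every patient scored, no covariates, common standardised effect. Units are SDs of the analysed outcome within age group.

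**Formula.** Detectable difference = 2.8 × sqrt(1/n treated + 1/n untreated). With equal treated shares, inverse-variance pooling of the two standardised estimates has the same precision as one comparison on all N.

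**Results with 40% treated**

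| N, adult share | Adults alone | Children alone | Combined |
|---|---|---|---|
| 150, 50% | 2.8 × sqrt(1/30 + 1/45) = 0.66 | 0.66 | 2.8 × sqrt(1/60 + 1/90) = 0.47 |
| 150, 40% | 2.8 × sqrt(1/24 + 1/36) = 0.74 | 2.8 × sqrt(1/36 + 1/54) = 0.60 | 0.47 |
| 150, 70% | 2.8 × sqrt(1/42 + 1/63) = 0.56 | 2.8 × sqrt(1/18 + 1/27) = 0.85 | 0.47 |
| 270, 50% | 2.8 × sqrt(1/54 + 1/81) = 0.49 | 0.49 | 2.8 × sqrt(1/108 + 1/162) = 0.35 |

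**Treated share.** At N = 150 the combined figure is 2.8 × sqrt(1/45 + 1/105) = 0.50 SD with 30% treated and 2.8 × sqrt(1/75 + 1/75) = 0.46 SD with 50%.

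**Standard error.** Relative to one age group holding a fraction f of the patients, the combined standard error is sqrt(f) times as large. For f = 0.5 it falls by 1 − 0.71 = 29%. With 70% adults it falls by 1 − sqrt(0.7) = 16% against adults alone and by 1 − sqrt(0.3) = 45% against children alone.

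**Raw pooling.** Suppose Protein C has no effect, the mean change is a in adults (SOFA) and c in children (PELOD), and adults make up q1 of users and q0 of non-users. The expected raw difference is q1·a + (1 − q1)·c − q0·a − (1 − q0)·c = (q1 − q0)(a − c). This is zero only if the age mix is the same in both groups or the two instruments change by the same number of points. The plan ensures neither.

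**The case against.** The strongest reply is that the plan makes no wrong choice here; it leaves one open. The Abstract and Section 8.3 name ΔSOFA and dPELOD separately, so raw pooling is the less natural reading. Reporting adults and children apart also suits the aim in Sections 7, 8.2 and 11 of finding subgroups that respond differently. Section 8.5 already concedes that treatment comparisons may be feasible for some endpoints only. At N = 270 one age group alone reaches 0.49 SD, close to the combined 0.47 SD at N = 150.

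Much of this stands:
- A reader might infer that every morbidity comparison uses about half of the registry. The documents do not say so. Section 8.7 commits to neither separate nor pooled analysis, and an equal age split is only a tentative forecast.
- A reader might take 0.66 against 0.47 SD, or the 29%, as the size of the loss. It is one scenario among several, on inputs the documents do not fix.
- A reader might conclude that the separate SOFA and PELOD results should give way to the combined one. The subgroup aim argues against that; they should stay, with confidence intervals.

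The reply does not answer the missing treatment term. Nor does it rule out mixing scales: the mortality model already treats APACHE II and PRISM III as if they were one covariate. And separate estimates alone do not provide the overall contrast that the objective implies.

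**Conclusion.** The point holds as an inexpensive improvement. Section 8.7 defines no Protein C contrast for the morbidity scores and no rule for joining the two instruments. Under a common standardised effect, a combined age-stratified contrast is more precise than either age group alone in every scenario shown. At 150 patients and 40% treated, the detectable difference moves from between 0.56 and 0.85 SD per age group to 0.47 SD, for adult shares of 40% to 70%.

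The absolute figures are optimistic. Scores are captured over 7 days in ICU (Section 8.4) and Section 6 puts mortality above 50%, so deaths and ICU discharges before day 7 will reduce the number scored. Covariate adjustment is not modelled, and unequal treated shares in the two age groups would change the combined figure. Greater precision is no protection against confounding by indication, which stratifying by age leaves in place.

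**What to change.** In Section 8.7:

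1. Name Protein C use (yes/no) as the treatment term in the baseline-adjusted linear model. Fit it within each age group, with the same confounders as the mortality model. The severity score is then APACHE II/SAPS II or PRISM III, never a mixture.
2. Report the separate SOFA and PELOD estimates with 95% confidence intervals.
3. Add one combined contrast: standardise each effect within its age group, pool by inverse variance, and report a treatment-by-age-group check beside it.
4. Where a rank test is used, replace the unstratified Mann-Whitney test with a van Elteren test stratified by age group. It ranks within age group and needs no common scale, but does not adjust for other confounders.
5. State that raw SOFA and PELOD points are not pooled, and reconcile the Abstract with the flowchart footnotes on patients aged exactly 16 so that the strata are defined.

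The cost is analysis-plan wording; all the data are already collected. The downside is that the combined effect is in SD units and assumes a similar direction of effect in adults and children. The retained separate results let readers check that.

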Research question and objectives	
 
Systematic acquisition, analysis and dissemination of information on incidence and prehospital/inhospital course of Purpura fulminans, (possible long-term follow up) and its relation to infectious agents (e.g. meningococcemia, streptococcus etc.)
 
Systematic acquisition, analysis and dissemination of information on current management of PF (sepsis bundles and replacement strategies – protein C, AT, etc.)
 
Systematic acquisition, analysis and dissemination of information on outcomes (morbidity, mortality) of PF with current management strategies, stratified for use or non-use of protein C
 

Design	Prospective multicenter registry derived from systematic data collection on the incidence and treatment of sepsis-associated Purpura fulminans
Population	Patients diagnosed with Purpura fulminans associated with severe sepsis

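### Section 8.7 specifies no baseline- and confounder-adjusted Protein C comparison for SOFA/PELOD, although morbidity by Protein C use is an objective

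*Combined protocol and SAP*

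**What the plan says.** The Abstract (Section 4) lists as an objective the "outcomes (morbidity, mortality) of PF with current management strategies, stratified for use or non-use of protein C". Section 8.1 gives special weight to comparing outcomes with and without Protein C, and Section 8.2 repeats the intention.

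Section 8.7 treats the two outcomes differently.

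- **Mortality:** a logistic regression is fitted "to compare the efficacy of the different treatments (e.g. with or without Protein C supplementation", with pathogen, severity score, laboratory values, age, sex and co-medication offered as covariates.
- **SOFA/PELOD:** changes and 7-day means "will be compared to the scores determined on admission (baseline" by two methods, a "Paired samples T-test" and a "Linear model with morbidity score baseline adjustment and alternative co-variables (e.g. hematological, coagulation or inflammatory parameters". Neither Protein C nor treatment is named.
- **All endpoints:** the closing paragraph adds that "Between-group comparisons will be preceded by distribution analysis (Shapiro-Wilk Test of normality", followed by "parametric (one-way ANOVA, T test) or non-parametric (Kruskal-Wallis, Mann-Whitney U-test) approaches". The groups are not defined and no adjustment is mentioned.

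Section 8.5 warns that a split by Protein C use may be feasible for some endpoints only, without saying which. Section 9 leaves the choice of treatment to the responsible physician.

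**The concern.** The Protein C contrast is written out, with confounders, for mortality but not for morbidity. An analyst following Section 8.7 would produce a within-patient change from admission, a baseline-adjusted model that need not contain treatment, and possibly an unadjusted group test. The first does not address Protein C. The second does so only if the analyst adds the term. The third addresses it without allowing for why patients were given Protein C.

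Section 11 feeds biannual evaluations into treatment recommendations from the Advisory Committee. A morbidity result on Protein C that rests on an unadjusted contrast, or on a fall from admission with no comparator, would be weak support for them.

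**Working it through.** The documents give no SD, correlation, effect size or power for SOFA or PELOD, so there is no planned figure to reproduce.

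**Inputs from the documents.** About 50 patients a year for 3 years gives 50 × 3 = 150. The significance level is 0.05, uncorrected (two-sided assumed). Scores are taken at baseline and days 1, 3, 5 and 7. Stated mortality is above 50%. Entry is by diagnosis, with no score threshold.

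**Assumptions not in the documents.** Score mean 10, SD 4, correlation ρ = 0.5 between baseline and follow-up, half of patients given Protein C. The SD of the change is then 4 × √(2 × (1 − 0.5)) = 4.

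**Step 1: what the paired test responds to.** Simulations with N = 150, 1,000 runs each and no Protein C effect gave:

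| Scenario | Mean change | Significant improvement | Significant, either direction |
|---|---|---|---|
| No selection, no drift | 0.0 | 3% | 6% |
| Entry only at score ≥ 8 | −1.0 | 92% | 92% |
| Entry only at score ≥ 10 | −1.6 | 99.9% | 99.9% |
| Entry at ≥ 8, natural worsening of 2 points | +1.0 | 0% | 91% |
| No selection, sickest 30% lost before follow-up | −0.9 | 65% | 65% |
| No selection, natural recovery of 2 points | −2.0 | 100% | 100% |

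The selection rows agree with theory. Entry at ≥ 8 puts the mean admission score 4 × 0.352/0.691 = 2.04 above 10, and the expected fall is (1 − 0.5) × 2.04 = 1.02. The test can therefore point either way without any Protein C effect. The scenarios are illustrations: the plan has no entry threshold, and the natural drift is unknown.

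**Step 2: the unadjusted between-group test.** With Protein C allocated independently of severity, a t-test on the change rejected in 4.3% to 5.7% of runs in every null scenario, so it is valid if the groups are comparable. Now let Protein C patients be sicker at admission by Δ points, with no effect of treatment:

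- the contrast in change is shifted by −(1 − ρ)Δ = −0.5Δ, which favours Protein C;
- the contrast in raw follow-up score is shifted by +ρΔ = +0.5Δ, which counts against it.

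The standard error is 4 × √(1/75 + 1/75) = 0.653. The rejection rates are:

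| Δ at admission | Shift | Unadjusted test | Baseline-adjusted model with Protein C term |
|---|---|---|---|
| 0 | 0 | 5% | about 5% |
| 2 | 1 | about 33% | about 5% |
| 4 | 2 | about 86% | about 5% |

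Which way the error runs depends on whether changes or raw scores are compared, which the closing paragraph of 8.7 does not say. Baseline adjustment removes only the part carried by the admission score; other reasons for giving Protein C need the remaining confounders.

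**Step 3: what the named term buys.** For an assumed 2-point effect with N = 150 and no imbalance, simulated power is about 94% for the adjusted model and about 85% for the unadjusted test (90% and 80% if 30% receive Protein C). SOFA and PELOD cover different ages, so 150 is too large for either alone. With 75 patients split equally, the standard errors are 4 × √(2/37.5) = 0.924 unadjusted and 4 × √0.75 × √(2/37.5) = 0.800 adjusted, and power is about 57% and 69%. All these power figures ignore early deaths and residual confounding.

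**The case against.** The strongest reply is that the comparison is already available. The closing paragraph of 8.7 covers all endpoints, SOFA and PELOD are listed endpoints, and Section 8.5 gives use versus omission of Protein C as its example of a dichotomy. The covariate list in the linear model is introduced as examples, so a treatment term is not excluded. A reader might infer that the plan cannot compare morbidity by Protein C use at all; the documents do not support that. What remains is that the available route is generic and unadjusted, and that an open list permits the term without planning it.

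A reader might also infer that the paired test is bound to show improvement through regression to the mean. That is not supported either. Entry is by diagnosis with no score threshold, baseline is ICU admission, and Section 6 describes a rapidly evolving disease, so scores may rise. One can assume that patients enter 4 points above their underlying level and find significance in 87% of registries with 40 patients or 99% with 75. The arithmetic is right, but it assumes the excess that it would need to show; with no excess and no drift the rate is about 5%.

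Finally, describing the course of disease is itself an objective, and change from admission serves it. Nothing in the documents says a within-patient fall will be read as Protein C efficacy. This is a reason to keep the paired summary as description.

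**Conclusion.** The point holds as a gap in specification. Section 8.7 does not define a baseline- and confounder-adjusted Protein C contrast for SOFA/PELOD, although the objectives and design call for morbidity by Protein C use. The paired test is uninformative about Protein C, the linear model does not name it, and the remaining between-group tests are unadjusted where physicians choose treatment.

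The size cannot be fixed from the documents. It depends on the assumed SD, correlation, Protein C share and severity imbalance, and the error may run in either direction: from none if the groups are alike at admission to roughly one false positive in three at a 2-point imbalance. With stated mortality above 50%, loss of later scores through death is at least as plausible a source of apparent improvement as regression to the mean, and 8.7 does not say how such deaths are handled. The matter should be corrected; it does not invalidate the registry.

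**What to change.** Amend Section 8.7 as follows.

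1. Make the main morbidity comparison a baseline-adjusted linear repeated-measures model of the scores at days 1, 3, 5 and 7, with terms for Protein C use, day, baseline score and the confounders offered for the mortality model, using baseline values. Run it separately for SOFA and PELOD.
2. Classify Protein C use by what was given before the score being analysed, so that later treatment does not explain earlier scores. Section 8.4 deduces exposure from doses over the whole ICU stay, which does not ensure this.
3. State how deaths before day 7 enter the analysis, for example by a worst-rank sensitivity analysis beside the analysis of survivors, and how other missing scores are handled.
4. Report the paired change from admission as description with a confidence interval, not as evidence on Protein C.

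With few patients per score, the confounder list should be short and fixed in advance. The cost is a modest amount of extra analysis and a few more model terms. No new data are needed: the flowchart in Section 8.2 already schedules the scores at baseline and days 1, 3, 5 and 7, and the treatment records from day 1. This assumes that the eCRF, which is not in the documents, records Protein C by those intervals.

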#### 4. Abstract

Title	Sepsis-Associated Purpura Fulminans International Registry - Europe
Short title (Acronym)	SAPFIRE
Rationale and background	
Purpura fulminans is the clinical manifestation of disseminated thrombosis in dermal and systemic microcirculation. This rare disease is frequently associated with multiple organ failure and represents a life-threatening condition with mortality exceeding 50 %. Apart from isolated idiopathic cases, deficiency of Protein C, a major intrinsic anti-coagulant, is considered the leading cause of Purpura fulminans. In the vast proportion of cases, the condition has been shown to emerge secondary to acquired Protein C deficiency associated with severe sepsis, mostly of meningococcal or pneumococcal origin.
 
A consistent therapeutic approach to sepsis-associated Purpura fulminans (SAPF) has not been established yet. With exaggerated pro-coagulant activity being confirmed as the key pathogenic aspect, several treatment modalities aiming at the balance restoration in the coagulation cascade have been considered. Based on the experience gathered in patients with inherited Protein C deficiency, supplementation with Protein C formulations has been used as adjuvant therapy in SAPF.
 
Most of the information on SAPF incidence and therapy has been obtained before 2004. Meanwhile, lack of comprehensive data poses considerable difficulties with regard to its diagnosis and treatment. SAPF causality might have been substantially altered in the wake of widespread meningococcal vaccination. There are neither evidence-based treatment guidelines nor comparative evaluation of the efficacy of different therapeutic approaches. Therefore there is a pronounced need of systematic data collection and evaluation covering several aspects of SAPF, such as epidemiology, causality, morbidity and therapy.

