## 6. Rationale and background

*Purpura fulminans* is a life-threatening and highly disabling condition characterized by rapidly evolving thrombosis in the dermal and systemic microcirculation. The estimated incidence of the disease is 0.1 per 100,000 inhabitants [Nicolas and Debonne, 2002]. It is associated with high mortality (above 50 %), owing to progressive cutaneous hemorrhage and multiple organ dysfunction. Profound tissue lesions and grave disturbance in numerous vital functions also determine a considerable long-term morbidity and disability.

Apart from a few cases of idiopathic origin, the etiology of *Purpura fulminans* is ascribed to either congenital abnormality or acquired deficiency of Protein C-operating anticoagulant pathways. The latter condition is in the vast majority secondary to an acute severe infection, thus coining the term sepsis-induced or sepsis-associated *Purpura fulminans* (SAPF) [Betrosian et al., 2006]. Several bacterial pathogens can induce SAPF, with meningococcal and pneumococcal infections accounting for the majority of cases. Causal involvement of viral and protozoan pathogens also has been described [Betrosian et al., 2006].

The pathogenesis of SAPF exemplifies the induction of a coagulopathy by the intertwined action of extrinsic bacterial (e.g. endotoxins) and intrinsic (e.g. vascular, inflammatory and hematologic) factors. The decay of endogenous anti-coagulant systems has a decisive contribution to the imbalance of clotting in sepsis and the presence of a consumptive coagulopathy is a distinct feature of infection-associated *Purpura fulminans* [Darmstadt, 1998]. Extensive similarities with clinical and pathological characteristics of *Purpura fulminans* in congenital Protein C deficiency have brought this endogenous anti-coagulant into focus with regard to the pathogenesis of SAPF [Francis, 1990]. Indeed, SAPF reflects an exaggerated pro-coagulant response resulting from decreased abundance/activity of endogenous anticoagulants, such as antithrombin and Protein C [Dempfle,

2004]. Meanwhile, ample evidence has accumulated in support of the view that circulating Protein C concentrations markedly decline in severe sepsis, due to both, suppressed biosynthesis and increased consumption/degradation [Fourrier et al., 1992; Leclerc et al., 1992; Borgel et al., 2006; Shorr et al., 2006].

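### Raw ICU, hospital, ventilation and renal-replacement days have no rule for death, so in between-group comparisons an early death counts as a short, favourable duration

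*Combined protocol and SAP*

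**What the plan says.** The endpoint list in section 4 gives durations as plain day counts, for example "Length of ICU stay (days") and "Duration of renal replacement therapy (days"), with hospital stay and mechanical ventilation in the same form. The flowchart in section 8.2 records these totals in its end-of-study column, at hospital discharge or in-hospital death.

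Section 8.7 fits a logistic model for in-hospital mortality, where death is the outcome. For other endpoints it promises descriptive statistics with confidence intervals, and then: "Between-group comparisons will be preceded by distribution analysis (Shapiro-Wilk Test of normality"). Depending on the result, t-test/ANOVA or Mann-Whitney/Kruskal-Wallis follows. SOFA and PELOD changes are examined by paired t-test and a baseline-adjusted linear model, and "their mean values calculated for the observation period of 7 days will be compared to the scores determined on admission (baseline"). Section 8.4 limits score capture to the time in ICU.

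On mortality, section 4 says the disease "represents a life-threatening condition with mortality exceeding 50" per cent, and section 6 repeats it: "It is associated with high mortality (above 50" per cent).

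Sections 4 and 6 to 8.9 contain no worst-rank rule, support-free-days definition, competing-risk method, survivors-only label or missing-score rule. Section 8.9 favours composite outcomes in general terms but defines none. It attributes the variability of hospital stay to recovery and surgery, without mentioning death.

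**The concern.** A stay can be short because the patient recovered or because the patient died. A t-test or rank test on raw days treats the two alike. With about half the cohort expected to die, a treatment group with fewer early deaths contributes more long survivor stays and can look worse on ICU days, hospital days and days of organ support.

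Sections 8.1 and 8.2 stress comparing outcomes with and without protein C, and section 11 says biannual evaluations feed therapy recommendations. It does not say which endpoints drive them. A reader of a raw-days comparison could not tell longer need for care from better survival.

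The scores raise a related but weaker issue. They stop at death or ICU discharge, so a change from baseline describes only the patients still being scored.

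**Working it through.** The plan gives no power, effect-size or duration figure, so there is nothing of its own to reproduce. The check is an illustration.

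**From the documents.** Mortality above 50% (sections 4 and 6). Enrolment "Approx. 50 patients/year" for 3 years (section 4): 50 × 3 = 150 patients. At 50% mortality, 150 × 0.5 = 75 of them have a duration ended by death. Significance level 0.05 (section 8.7).

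**Assumed, because the documents are silent.** Mortality 45% vs 55%. 75 patients per group. Stay distributions identical in both groups given vital status. Survivors' ICU stay lognormal, median 14 days, log-SD 0.6. Time to death exponential with median 1, 2, 4 or 8 days, or lognormal (log-SD 0.6) with median 14 or 20 days for the late-death cases. Tests are two-sided, so the nominal rate in one direction is 2.5%.

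**Formulas.**
- Survivors' mean S = 14 × exp(0.6²/2) = 16.76 days.
- Decedents' mean D = median / ln 2 (exponential), or median × exp(0.18) (lognormal).
- Group mean = p × D + (1 − p) × S, where p is mortality.
- Gap (fewer-deaths group minus other group) = (0.55 − 0.45) × (S − D).

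| Median time to death (days) | D | Mean stay, 45% vs 55% mortality | Gap (days) | Fewer-deaths group's stay significantly longer (Mann-Whitney) |
|---|---|---|---|---|
| 1 | 1.44 | 9.9 vs 8.3 | +1.5 | 17–18% |
| 2 | 2.89 | 10.5 vs 9.1 | +1.4 | 16–17% |
| 4 | 5.77 | 11.8 vs 10.7 | +1.1 | 10–12% |
| 8 | 11.54 | 14.4 vs 13.9 | +0.5 | 5–6% |
| 14 (lognormal) | 16.76 | 16.8 vs 16.8 | 0.0 | about 3% |
| 20 (lognormal) | 23.94 | 20.0 vs 20.7 | −0.7 | about 1% |

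The percentages are simulated; ranges show the spread over repeated runs. With equal mortality and equal time to death, the rate returns to nominal.

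**Ventilation.** Assume survivors are ventilated for 60% of their stay (0.6 × 16.76 = 10.06 days) and decedents throughout. The gap is 0.10 × (10.06 − D) = +0.86, +0.72, +0.43 and −0.15 days for median time to death 1, 2, 4 and 8.

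**Other inputs.** With survivor means of 10 to 30 days, decedent means of 2 to 5 days and log-SD 0.8, the gap at 55% vs 45% is 0.5 to 2.8 days, with wrong-direction significance in 6% to 19% of runs. At 60% vs 40% it is 1.0 to 5.6 days and 19% to 55%.

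**Scores.** Assume 35% vs 45% dead by day 7, identical trajectories and 0–12% of survivors already off ICU. The fewer-deaths group then looks worse on day-7 change by 0.2–0.7 points if the hazard follows the current score, and by about zero if it follows baseline only. A false finding of worse occurs in 4–6% of runs at 38 per group (5–9% after baseline adjustment). The 7-day mean shifts by 0.00–0.08 points on an SD of about 4. The paired day-7 change with no true mean change (40% dead by day 7, 75 patients per instrument) runs from −2.8 to +1.5 points, depending on who dies and who is discharged. None of the results with a current-score hazard and 12% off ICU is significant.

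**The case against.** **No committed analysis.** Section 8.7's only explicit treatment-comparison model is for mortality. Section 8.5 expects comparisons on selected endpoints only, and section 8.9 gives hospital stay an economic purpose, for which raw days including deaths are correct. A reader might infer that the registry will compare durations by protein C use; the documents do not say so. What remains is that sections 8.1 and 8.2 and the generic between-group sentence allow it, and the selected endpoints are never named.

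**Silence is not a rule.** Section 8.7 does not state that deaths keep their raw days. That is the natural reading of a plain day count, but still an inference.

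**Favourable inputs.** The documents give no mortality by group, time to death, stay by vital status or treatment split. At 47.5% vs 52.5% with median time to death 4 days, wrong-direction significance is 5%. At 45% vs 55% with the same median, an unequal split lowers it to 10% (30:120) or 7% (20:130). This stands, and limits how firmly the size can be stated. A reported mortality result would also help a careful reader interpret a longer stay.

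**Scores.** A reader might infer that the SOFA/PELOD group comparisons are equally distorted. The figures do not support that, and the paired t-test makes no treatment claim.

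**Overlap.** With about half the patients tied at worst, a death-inclusive endpoint partly repeats the mortality analysis. That is true, and a real cost.

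**Conclusion.** The concern holds for durations: no rule covers death, and raw days can make a group with fewer early deaths look worse. The illustrated size is 1.5 to 0.5 days, with wrong-direction significance in about 18% to 5% of runs against 2.5%. It rests on an assumed ten-point mortality difference, equal groups and early deaths.

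It would go too far to say that raw days always penalise the life-saving treatment. The bias needs a group difference in mortality or in time to death, and it vanishes or reverses if deaths come as late as, or later than, survivors' discharge. The documents do not show which case applies, which is the reason to set a rule before results are read. Nor does the problem reach the mortality model, where death is the outcome.

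For the scores, only labelling and reporting need to change. This should be fixed; confidence is medium because every quantitative input beyond overall mortality and enrolment is assumed.

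**What to change.** In section 8.7:

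1. For any between-group comparison of durations, such as protein C use vs non-use, replace raw days with one of two endpoints. The first is days alive and free of ICU, ventilation or renal replacement over one fixed window, with death scored 0 and the post-discharge assumption stated. The second is an ordering with in-hospital deaths tied worst and survivors ranked by fewer days. Adjust for the same confounders as the mortality model. Section 8.7 says only that these "can be included as covariates in this model", so state which are used. Keep raw durations, including hospital stay for economic burden, as description by vital status.
2. Label the SOFA/PELOD paired t-tests and the 7-day mean as descriptive in patients still observed, and draw no treatment conclusion from them. Report the numbers dead, discharged and scored at each score day. A death-inclusive ordering of scores is an optional sensitivity analysis.

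Cost: analysis wording and derived variables. Vital status and total days are already in the flowchart; ICU status on each score day should be confirmed in the eCRF. Fixed-window days need the stated assumption because follow-up ends at hospital discharge. The new endpoint overlaps with mortality, is less direct to interpret, and adjustment cannot remove unmeasured confounding where the physician chooses treatment (section 9).
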